Study Design	In this single centre study, assessment of three theoretical enhancements to visual acuity testing 1) crowding-enhanced letters, 2) crowded-enhanced contrast-modulated letters and 3) measurement of crowding distance, will be tested using clinical tests in a control group and in amblyopic children. Results from these 3 tests will be compared to each other and to those from the Sonksen logMAR Test (SLT) the current clinical standard, as measured by a clinician. Comparisons across test, and between participant groups, will enable us to determine the optimal test, or combination of tests, for detecting amblyopia. Visual acuities and crowding distance will be measured prospectively in a randomised controlled trial. Results will also be obtained in a control group, a sample of false-positive referrals to the hospital, and compared to that already obtained on normal healthy children (Waugh et al., 2018).					
	The testing will take place in a clinical room neighbouring the ACPOS (Addenbrooke's Community Paediatric Ophthalmology Service) clinic, which is hosted within the University Eye Clinic at Anglia Ruskin University (ARU).					
Study Participants	Test participants; 42 Male and female, 3 to 11-year-old children diagnosed as having amblyopia (21 strabismic and 21 anisometropic) by clinicians within Addenbrookes Community Paediatric Ophthalmology Service (ACPOS), hosted by the University Eye Clinic at Anglia Ruskin University (ARU) will be recruited.					
	Control Participants; 21 Male and female, 3 to 11-year-old children who have either been falsely referred into ACPOS (Addenbrookes Community Paediatric Ophthalmology Service) by the national vision screening service, but who are subsequently found to have satisfactory visual function; or visually healthy volunteers who have already passed vision screening will be recruited.					
	All participants must be able to perform the Sonksen logMAR Test (SLT) either verbally, or by using a matching card.					
Planned Size of Sample (if applicable)	Total participant pool: n =63 Anisometropic amblyopes n =21; Strabismic amblyopes n =21; Control group n =21.					

Follow up duration (if applicable)	This project requires one visit by each participant. However participants may choose to participate more than once (up to a maximum of 3 times) during the recruitment and testing period (within the 2 year data collection period).

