Planned Study Period	It is planned that recruitment and testing will take place over 2 year period. (See Gantt Chart for estimated project delivery dates).
Research Question/Aim(s)	This study aims to investigate whether proposed modifications to visual acuity tests will offer better sensitivity to the detection of amblyopia than the Sonksen logMAR test (SLT). It will also determine whether differences in outcomes occur for anisometropic, versus strabismic amblyopes.

FUNDING AND SUPPORT IN KIND

FUNDER(S) (Names and contact details of ALL organisations providing funding and/or support in kind for this study)	FINANCIAL AND NON FINANCIALSUPPORT GIVEN				
 Anglia Ruskin University (via The Doctoral School) [name] Director of Doctoral School Research and Innovation Development Office Anglia Ruskin University, Chelmsford [name] [contact] 	The Research Supervisor/Chief investigator ([name] [name]) has been awarded a Vice Chancellor's Studentship to provide fees and a living stipend to support a PhD student, ([name]), throughout the course of this study.				
[contact] 2) Anglia Ruskin University via Quality Related Research Funds from HEFCE (Higher Education Funding Council for England) to FST and Anglia Vision Research.	Quality Related Research Funding from HEFCE awarded to ARU has been approved for the Research Supervisor to reimburse participants' parents/carers for their time (£10 per participation visit in the form of an amazon voucher) for this project.				
[name] Deputy Dean (Research and External Income) Faculty of Science and Technology Anglia Ruskin University [name] [contact]	Quality Related Research Funding has been approved for the Research Supervisor to cover the cost of computer hardware and software required for the execution and analysis of data generated from this project.				

Contact on behalf of the Sponsor

[name], Chair of Faculty of Science and Technology Research Ethics Panel (FST FREP), Department of Psychology, Faculty of Science and Technology, Anglia Ruskin University, Cambridge [name] [contact]

ROLE OF STUDY SPONSOR AND FUNDER

The Sponsor and the Funder for this project is Anglia Ruskin University (ARU).

The Principle Investigator on this study is a PhD student ([name]) funded through an ARU Vice-Chancellor's PhD Studentship, awarded to the Chief investigator / Research Supervisor ([name] [name]). The award funds the PhD student's fees and bursary.

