In the Sonksen logMAR Test (SLT), a single line of 4 letters separated from each other by 5 stroke-widths (or 1 optotype width), is contained within a box, separated from the letters also by 5 stroke-widths.

Recognition of target optotypes created by contrast-differences (second-order stimuli) is prone to greater crowding effects than is recognition of optotypes created by luminancedifferences (first-order stimuli) (Wong, Levi and McGraw, 2001, 2005; Chung, Li and Levi, 2008; Hairol, Formankiewicz and Waugh, 2013). This effect is present in normal vision, however even greater visual losses for contrast-defined targets, as well as stronger crowding effects, have been reported in amblyopia (Chung, Li and Levi, 2008). By presenting a contrastmodulated (CM) target letter (H, O, T or V) surrounded by four other letters (U, A, L, C) placed 1 stroke-width away (in the modified Cambridge Crowding Test arrangement), this research aims to examine whether this second-order vision test will exaggerate differences between the eyes of amblyopic children, when compared to those measured in visually 'normal' children. The results will again be compared to those obtained with the Sonksen logMAR test (SLT), a first-order vision test, to compare their sensitivities to amblyopia detection.

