Finally, crowding distance, the spatial distance over which crowding occurs, in normal foveal (central) vision is small (2-4 arcmin) and cannot be measured with current standard clinical optotypes due to their large size (5 arcmin for 0.0 logMAR acuity) (Danilova and Bondarko, 2007; Huurneman et al., 2012; Siderov, Waugh and Bedell, 2013; Pelli et al., 2016). To get around this difficulty, a new vision test was recently created to quantify the crowding distance or "critical spacing" of crowding (Pelli, Waugh, Martelli et al., 2016). It uses a new "Pelli" font (see Figure 3), which is much thinner horizontally than standard clinical fonts, allowing the optotypes to get closer to each other in physical space. This 'Crowding Distance Test' permits quantification of the critical spacing of crowding for the first time in a clinical population. The new "Pelli" font, each optotype appearing like tall skinny numbers, has already been trialled on 'visually normal' school-aged children (Waugh et al., 2018), but not yet examined on children with greater sensitivity to visual crowding, i.e., amblyopes. The third vision test in the proposed research, will investigate whether or not "crowding distance" measures made in each eye, results in greater inter-ocular differences, leading to better detection of anisometropic and strabismic amblyopia than does the current clinical standard visual acuity test, the Sonksen logMAR test (SLT).

8

Figure 3: 'Pelli' font

By using closer first-order target optotypes, second-order target optotypes, and quantifying crowding distance in paediatric populations, the ability to detect amblyopia and monitor amblyopia treatment, could be significantly improved for the first time since the 1960s. At that time crowding was first quantified in a clinical population of adult amblyopes (Flom, Weymouth and Kahneman, 1963) and was subsequently incorporated into commercially available tests as best practice.

THEORETICAL FRAMEWORK

Clinical Appointment with clinical vision test (SLT) Identification and recruitment of amblyopic and control particpants

Vision tested with modified vision tests

Analysis of results

Research questions and aims

Research question:

"Do the new vision test modifications offer better sensitivity to detection of inter-ocular difference leading to improved detection and monitoring of amblyopia, than the Sonksen logMAR test (SLT)?

Secondary research question:

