In this single centre study results from the 'Enhanced Cambridge Crowding Test', 'Contrastmodulated Cambridge Crowding Test' and the 'Crowding Distance Test' in their ability to detect amblyopia will be assessed using a prospective quantitative randomised controlled design. The results obtained from the experimental groups (anisometropic and strabismic amblyopia) will be compared to Sonksen logMAR test (SLT) results (assessed and documented by the ACPOS clinicians). They will also be compared to those obtained in this study from a control group. The testing will take place in a clinical room neighbouring the ACPOS (Addenbrooke's Community Paediatric Ophthalmology Service) clinic, which is hosted within the University Eye Clinic at Anglia Ruskin University (ARU).

Study procedure

Prospective participants will be identified by their clinician at their ACPOS clinical appointment, and given participant information leaflets. Healthy volunteers will also be accepted as control participants and given participant information leaflets. All participants will be required to provide informed assent, and their parent/guardian provide written informed consent before the experiments are conducted and after the nature and consequences of the study are explained. COVID tracking consent forms The recruitment and consent process will be monitored by the Principal investigator within the University Eye Clinic at ARU.

All tests will be conducted with the child's corrective lenses if required, after consent and assent is achieved. The child's Ophthalmology clinical team will be informed of their participation by use of an addendum into the clinical notes, if recruited through the ACPOS clinic. To reduce the risk of potential exposure to COVID-19 by participants during testing, the researcher will wear an apron and a mask. The researcher, participant and parent will wash their hands upon entering the testing room (which has its own sink and sanitising soap) and wear masks (Medical F2 as per ACPOS clinical protocol). Children under 11 may choose to not wear a mask. Individual risk assessments are conducted at the time of appointment creation by ACPOS/Addenbrooke's staff. All high-risk participants and parents will NOT have appointments entered into the recruitment system. All participants are children, so risk is minimal. All equipment will be Clinell wiped before and after use. Disposable occlusive patches and social distancing will also be used throughout testing.

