Following completion of the vision tests, participants will be asked if they wish to be involved again with the study. If they do, then they will be tested again following their next Orthoptic review with the ACPOS clinic, or at a time that suits the family best. If they do not, this is the end of their participation.

Consideration of measurement tools, validity and reliability

The results will be generalizable to the entire UK screening population of 3 to 11-year-olds, due to the use of a control group, ensuring external validity.

Participant bias will be controlled and intra-observer reliability maximised using the rigorous set of forced-choice psychophysical testing procedures described above and a single specialized researcher. The researcher is a qualified clinical Orthoptist with many year's experience working with children in vision screening clinics, ensuring that the results will be obtained as accurately and consistently as possible. Test/re-test reliability is ensured by the use of randomization of the order in which the eyes are examined, and counterbalancing the order of the experiments.

Statistical consideration and Data management and analysis

Anonymised data from the 3 experiments will be stored digitally on the experimental computer, which is password protected and only accessible to members of the research team. Data will be compiled in an Excel spreadsheet, ready for analysis.

The data will be analysed using SPSS or Statistica with Repeated Measures Analysis of Variance models. Visual acuities, crowding and critical spacing estimates will be compared between normal and amblyopic groups. Confirmation of normality and sphericity will be assessed with a Shapiro-Wilk test and Mauchley's Test of Sphericity and where necessary, error rates will be adjusted with a Huynd-Feldt Correction in order to ensure that type 1 errors (incorrect rejection of the null hypothesis) are less likely. The rate of improvement of visual acuity, crowding and critical spacing over the treatment period will also be compared (in those participants who opt to complete more than one assessment session) between the three modified tests, and the SLT.

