The clinician will notify the researcher if the participant wishes to take part, or the participant can contact the researcher directly using the details on the information leaflet. The researcher will then discuss the research with the prospective participant and their parent/guardian, giving opportunity for further questions to be asked and answered. If the participant and their parent/guardian demonstrate understanding of the requirements of the study and wish to consent to take part, the parent/guardian will be given a consent form to sign, and a record of clear assent will be taken from the participant (Appendix 1). Both parental consent and clear participant assent must be obtained in order for the participant to be recruited. Once consent and assent are provided, the researcher will add an addendum to the participant's clinical notes to inform clinicians. This will again ensure that the participant is not repeatedly approached as a potential participant.

While participants will not be paid for their participation in the study, they will be offered a £10 Amazon gift voucher as compensation for their time as a result of participating in the study.

Ethical considerations

This research will be conducted in full conformation with the principles of the "Declaration of Helsinki", Good Clinical Practice (GCP) and within the laws and regulations of the United Kingdom; and on approval by Anglia Ruskin University and the local NHS research ethics committee (REC). Prior to recruitment, participants will be given full written information about the study, in order to allow them to make an informed decision as to whether or not they wish to participate. Participation will require both signed informed consent from a legal guardian and informed assent from the child following the provision of age appropriate written information. Participants can also withdraw from the study at any point without any given reason, without prejudice.

The sensitivity of the new tests, compared with the existing SLT test, will not be known until data analysis is complete. If the data suggest that the new tests provide additional useful clinical insight into the participant's visual condition, this information will be shared with the Ophthalmology clinical team to ensure the participants continue to receive appropriate management.

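### The plan promises to rank tests, and combinations of tests, on detecting amblyopia, but its analyses compare only means, rates of improvement and agreement

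*Combined protocol and SAP*

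**What the plan says.** The detection aim appears in four places.

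- Synopsis, Study Design: comparisons across tests and groups are to "determine the optimal test, or combination of tests, for detecting amblyopia".
- Synopsis, Research Question/Aim(s): the question is whether the modified tests offer "better sensitivity to the detection of amblyopia than the Sonksen logMAR test (SLT").
- Rationale, on the contrast-modulated test: results will be set against the SLT "to compare their sensitivities to amblyopia detection".
- Study design: the three tests "in their ability to detect amblyopia will be assessed using a prospective quantitative randomised controlled design".

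The Rationale also gives the link it relies on, for the crowding distance test: "greater inter-ocular differences, leading to better detection of anisometropic and strabismic amblyopia". Under Ethical considerations the protocol adds: "The sensitivity of the new tests, compared with the existing SLT test, will not be known until data analysis is complete".

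The analysis is in the section on statistical consideration and data management. "The data will be analysed using SPSS or Statistica with Repeated Measures Analysis of Variance models", and "Visual acuities, crowding and critical spacing estimates will be compared between normal and amblyopic groups". Rates of improvement are compared in children with repeat visits, and Bland-Altman analysis covers agreement between tests. The Sample Size section adds Tukey or Dunnett comparisons. The documents give no positivity threshold for the new tests, no sensitivity, specificity or ROC analysis, no model that combines tests, and no rule for calling a test optimal.

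**The concern.** A comparison of means shows whether amblyopic and control children differ on average on a test. Detection concerns individuals: what share of amblyopic children lie beyond a cut-off that few controls exceed. That depends on the size of the IOD relative to its spread in both groups. If spreads differ between tests, the test with the larger mean IOD need not detect better. Bland-Altman analysis shows whether two tests give similar values, not which of them separates the groups.

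Scale is a further obstacle. The letter tests yield logMAR acuity, whereas the crowding distance test yields a spatial distance, which the Rationale quotes in arcmin. The plan names no common scale and no standardised difference for comparing the tests.

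Followed exactly, the study would report which means differ and how far the tests agree. It would leave unanswered which test detects best and whether combining tests helps. If cut-offs, the IOD definition and a combination were chosen after seeing 63 children, the results would tend to be optimistic.

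**Working it through.** **1. The plan's own figures.** For Hypothesis 1, effect 0.100 and SD 0.100 logMAR give d = 1. With two-sided alpha 0.05 and power 0.8, n = 2 × (1.960 + 0.842)² / 1² = 15.7, so 16 per group as stated (an exact t calculation gives 78.1% power at 16). For Hypothesis 2, one-way ANOVA with three groups, f = 0.4 and 21 per group gives 79.8% power by the noncentral F, against the stated 80%. Both figures reproduce, and both concern means only.

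**2. Aim against analysis.**

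| Stated aim | Planned analysis that answers it |
|---|---|
| Size of the IOD, new tests v SLT (Hypothesis 1) | ANOVA on the IOD can |
| Subtype difference (Hypothesis 2), read as size of the IOD | ANOVA with post-hoc tests can |
| Ranking of tests on detection | None |
| Best combination of tests | None |

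**3. Illustration of why means do not rank detection.** The documents give no SD for each test, so the following are assumptions.

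- Per-eye SDs are 0.10 and 0.06 logMAR. The Sample Size section quotes both values, the first for planning and the second from a staircase study in children, but assigns neither to a particular test.
- Mean true IOD is 0.20 in amblyopes on both tests and 0 in controls.
- Between-child SD of the true IOD in amblyopes (τ) is 0 or 0.1.
- IOD is unsigned in both groups, because controls have no amblyopic eye.

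Control spread is s0 = per-eye SD × √2, giving 0.141 and 0.085. Amblyope spread is s1 = √(s0² + τ²): 0.141 and 0.085 at τ = 0, and 0.173 and 0.131 at τ = 0.1. The cut-off for 90% specificity is c = 1.645 × s0, giving 0.233 and 0.140.

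Sensitivity = 1 − Φ((c − 0.20)/s1) + Φ((−c − 0.20)/s1). AUC is the probability that an amblyope's unsigned IOD exceeds a control's, found by numerical integration.

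| τ | AUC, SD 0.10 v 0.06 | Sensitivity at 90% specificity |
|---|---|---|
| 0 | 0.73 v 0.91 | 41% v 76% |
| 0.1 | 0.73 v 0.85 | 43% v 68% |

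**4. What the means show in the same setting.** At τ = 0, mean unsigned IOD is 0.210 v 0.201 in amblyopes and 0.113 v 0.068 in controls. The group differences are 0.097 and 0.133, so the group-by-test contrast is 0.036. At τ = 0.1 they are 0.221 − 0.113 = 0.108 and 0.207 − 0.068 = 0.139, a contrast of 0.031. Simulating trials of 42 v 21 with independent test noise, a two-sided 5% t-test of this contrast is significant in about 13% (τ = 0) and 11% (τ = 0.1) of trials.

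**5. Precision of an added ROC analysis.** Hanley-McNeil: SE² = [A(1 − A) + (n1 − 1)(Q1 − A²) + (n2 − 1)(Q2 − A²)] / (n1 n2), with Q1 = A/(2 − A) and Q2 = 2A²/(1 + A). With 42 v 21, the 95% half-width is 0.096 at AUC 0.84 and 0.129 at AUC 0.71. By subtype (21 v 21) it is 0.123 and 0.157. Specificity of 19/21 has a Wilson 95% interval of 71-97%.

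**The case against.** The strongest reply is that the documents mostly use sensitivity to mean the size of the IOD. The research question and Hypothesis 1 are worded that way, the Rationale asks whether a test exaggerates the difference between eyes, and the synopsis says the optimal test will emerge from comparisons across tests and groups, which is what the ANOVA does. Much of this stands. A reader might infer that the planned analysis answers none of the hypotheses; the documents do not support that. Nor does the ethics sentence clearly promise a detection rate at a given false-positive rate, since it too can be read as the size of the IOD. That reading cannot, however, cover a best combination of tests, or the step from a greater IOD to better detection.

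It can also be said that comparing each test with controls already weighs the difference against spread. It does so within a test, but no standardised difference is to be reported or compared across tests.

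The illustration is built on unequal SDs and equal means, so it shows what could happen, not what will. A reader might infer that a contrast of means would be significant only at the 5% chance rate, or that the gap in detection becomes small when amblyopes vary widely. Both inferences rest on a signed IOD (amblyopic minus fellow eye), which has no counterpart in controls. With an unsigned IOD, the contrast exceeds the chance rate because noise raises the control mean. The gap also persists at τ = 0.3 (AUC 0.78 v 0.86, sensitivity 56% v 71%). Values of 0.2 and 0.3 are left out of the main range because, with a normal distribution, Φ(−0.20/τ) = 16% and 25% of amblyopes would have the better vision in the amblyopic eye.

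Finally, an accuracy comparison with the SLT would be biased as well as imprecise, because SLT acuity helps assign groups. That stands. It limits what the added analysis can claim and makes narrowing the aim a full alternative.

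**Conclusion.** The mismatch is real but limited. The aims of ranking tests on detection and of finding a combination have no matching analysis. Hypothesis 1, and Hypothesis 2 if sensitivity means the size of the IOD, can be addressed as planned, and the ANOVA and its sample size remain sound for means. This should be corrected, but it does not invalidate the planned analysis.

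That no accuracy or combination analysis is planned follows from the text alone. The size of the effect does not: under the assumptions in the working, tests with equal mean true IOD differ by 25 to 35 percentage points in sensitivity at 90% specificity (68 − 43 and 76 − 41), while the contrast of means would usually miss it. Tests with similar spreads would show a smaller gap.

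**What to change.** Make one of two changes.

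(a) Narrow the aim in the synopsis (Study Design and Research Question/Aim(s)), the Rationale and the Study design section to the size of the IOD, and drop the detection and combination claims. This costs only wording and fully reconciles aim and analysis.

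(b) Keep the ANOVA and add a descriptive analysis to the statistical section, for example:

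*For each test we will report the ROC area of the IOD (amblyopes v controls, and each subtype v controls) and the sensitivity at one pre-stated specificity common to all tests, with 95% confidence intervals. The IOD will be unsigned in both groups. The paired difference in ROC area from the SLT will be reported as an estimate only. Any combination of tests will be assessed by cross-validated logistic regression and labelled exploratory.*

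A specificity near 90% corresponds to 19 of 21 controls. The text should also state that SLT acuity is among the background items used to assign groups, so the comparison is tilted towards the SLT.

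Option (b) uses data already collected, with no extra children or visits. Its downside is imprecision: about ±0.10 to ±0.13 on an AUC between 0.84 and 0.71 with 42 v 21, wider by subtype, and 71-97% on a specificity of 19/21. No confirmatory claim about detection should follow from it.
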